B: As discography is not required in the inclusion criteria, disc levels will be determined by clinical and image findings. MRI findings of high intensity zone, modic changes type 1 or 2, and decreased T2 disc signal will be used [29-32] in conjunction with the general location of pain and tenderness on exam (upper, middle or lower lumbar location).

Treatment:

Intradiscal injection: The patient will be placed in a prone position in an outpatient fluoroscopy suite. Strict sterile technique will be observed. The lower back will be cleansed with chlorhexidine mixed with alcohol and covered with a sterile drape. A standard posterolateral extrapedicular discogram technique will be used under intermittent fluoroscopic imaging for each level previously determined to be a presumptive pain generator either clinically or through prior discography. The skin and superficial tissues will be anesthetized with 2-5 ml of lidocaine 1%. The needle tip of a 22-gauge or 25-gauge needle with stylet, single or double needle technique, will be directed toward the disc into Kambin's triangle. Depending upon the patient's tolerance of the procedure, one ml lidocaine 2% may be injected just outside the disc annulus. The stylet will then be replaced and directed into the disc nucleus. A volume of 0.6 ml of contrast solution consisting of 0.4 ml Omnipaque 240 or 300 contrast agent with 0.2 ml of cefazolin 330 mg/ml (for a total of 66 mg at a final concentration of 18 mg/ml based upon 3.5 ml total volume) (or in cefazolin allergic patients 0.4 ml of 40 mg/ml gentamicin) will be injected to confirm intranuclear location and for discitis prophylaxis.

Then, 2-3 ml of previously prepared autologous BMC will be injected into the disc. Thus, a total volume of 2.6-3.6 ml will be injected into each of the presumed pain generating discs during the treatment. There may be instances when the disc cannot accommodate the full volume of BMC due to high pressure (based on manual pressure estimation) or leakage into the epidural space. It may be necessary for the clinician to inject less than the 2ml of BMC. At least 1ml of BMC will

need to be injected into a disc to be considered a completed treatment. If the patient is experiencing a great deal of discomfort during the BMC injection, the physician may add 0.2 to 0.5 ml of ropivacaine 0.2%-1%. After the solution is injected, the needle will be removed. The alcohol and chlorhexadine will be cleansed from the patient's back and the drape will be removed. The patient will then either ambulate with assistance or be transported via wheelchair to the recovery room.

Placebo treatment procedure:

As it was not felt ethical to puncture a disc for a placebo treatment [32], it was elected to use an intramuscular injection of 3ml of normal saline on the dorsal surface of the corresponding proximal transverse process. For example, if the L5/S1 disc was the "treatment" disc, the corresponding placebo will be an injection of 3ml of normal saline just dorsal to the L5 transverse process. This will be performed for each disc level to be "treated".

The patient will be placed in a prone position in an outpatient fluoroscopy suite. Strict sterile technique will be observed. The lower back will be cleansed with chlorhexidine mixed with alcohol and covered with a sterile drape. The patient shall be draped in a manner that injection is not visible even if the patient looks behind to observe. The skin will be anesthetized with 2ml lidocaine 1% at each level to be injected. A 22 g spinal needle will be advanced to the transverse process at the superior level of each disc to be "treated". One ml of contrast agent, omnipaque 240, will be injected. Then, assuming an appropriate intramuscular contrast pattern, 3ml of normal saline shall be injected just dorsal to the transverse process. After the normal saline is injected, the needle will be removed. The alcohol and chlorhexadine will be cleansed from the patient's back and the drape will be removed. The patient will then either ambulate with assistance or be transported via wheelchair to the recovery room.

Rationale for non-intradiscal placebo: In light of theoretical risk of needle injury to the disc [32], it was not felt to be appropriate to have the placebo involve a direct disc injection of normal saline. A normal saline injection into the epidural space using an infraneural (retro-discal) transforaminal needle position as a potential placebo was also considered but felt also to be in appropriate due to the risk of unintentional needle position. The risk of disc puncture with this technique is 5% as well the risk of intrathecal injection is 3% [36]. In addition, a normal saline injection into the epidural space might have some dilutional therapeutic benefit as inflammatory cytokine have been documented in the epidural space [37] and therefore, normal saline may have a dilutional therapeutic benefit.

The patient will be observed clinically for 30 minutes with vital signs obtained upon initially arriving to the recovery room and then every 15 minutes. The patient will be discharged to a companion with written and verbal instructions to include no driving or operating machinery for 12 hours. They will be instructed to call for any concerning symptoms such as redness, swelling, fever, or increase in pain. They will also be instructed to call for any bowel or bladder problems, worsening of low back symptoms beyond day 2, post-treatment severe low back pain at any time, new onset fever, or new or worsening of any lower extremity symptoms. They will be

given clear written and verbal instructions on how to contact our providers with 24 hour availability. They will be offered a prescription for post-procedure pain medication, unless they currently have such medication, such as hydrocodone/ acetaminophen 5/325 mg or oxycodone/ acetaminophen 5/325 mg to take 1-2 tabs q 4-6hrs prn post-procedure pain, #10-20. They will be instructed not to engage in any strenuous activity for two weeks after the treatment.

Anticipated procedure time 60-90 minutes.

The patient will be contacted by telephone during post-treatment week one to monitor for any concerning symptoms or adverse events. The patient will be seen in our office for routine follow-up at post-treatment week 2, 4, and 8 weeks to assess for any adverse events and to monitor progress. At baseline 3,6,and 12 months the patients will complete the VAS, ODI and Global Perceived effect (GPE not performed at baseline) [35,38]. Patients will be seen more frequently if clinically indicated.

A medication query shall be performed at baseline 3, 6, and 12 months. In addition, any additional treatments obtained during the follow up period shall be recorded. Other treatments during the study period will be discouraged but not forbidden.

Alternatives to bone marrow concentrate treatment:

- These patients have typically had extensive conservative treatment and may be considering lumbar fusion surgery (or disc replacement) as a possible treatment option. The risks of this type of surgery in the lumbar spine include infection, bleeding, nerve injury, paralysis and death. The most common adverse event or outcome encountered, however, is perceived lack of efficacy or worsening of symptoms after this extensive surgery and recovery period.
- Although these patients have had inadequate pain relief and functional improvements from their prior conservative treatments, they certainly have the alternative of continuing with their current treatment regimen, which may be of some benefit. These treatments often include medications, physical therapy, chiropractic care, and spine injections. The risks of spinal injections, although rarely occurring, include infection, bleeding, nerve injury, paralysis, and death. The risks of the various medications used for pain are medication dependent and are numerous.
- Other types of intradiscal injections are an option. Intradiscal methylene blue has shown early promise in a quality RCT [11] but investigations to replicate their results have been disappointing [12, 13]. Intradiscal steroid may be of benefit for individuals with certain end plate changes on MRI [39] but these positive results have been viewed with extreme caution based on poor results from prior studies [40]. Other regenerative type treatments such as platelet-rich plasma may be also be beneficial [15, 16]. The risks of intradiscal injections, although rare, include infection, bleeding, nerve injury, paralysis, and death.

- “Alternative” or “complementary” medicine treatments such as acupuncture, prolotherapy or homeopathic remedies could also be considered. Serious risks of prolotherapy include paralysis and severe risks of acupuncture include pneumothorax.
- The option of no further treatment may also be a reasonable alternative for some patients.

5B. Analysis of study results:

The data from the pre and post VAS (0-100 mm) and Oswestry disability index 0-100 will be analyzed from baseline to 3, 6, and 12 months [35]. Categorical data will be used. Primary outcome for success will be considered at least 50% improvement in pain by VAS at 6 months and secondary outcome at 3 and 12 months. Additional secondary outcomes will include 3, 6, and 12 month minimum of 30% improvement in ODI. Further secondary outcomes will also include a minimum of 30%, and 70% improvement in pain at 3, 6, and 12 months. All time point categorical success rates will be compared to placebo group with 95% CI determined. Group data mean pain scores will also be analyzed for each time point using *t*-tests. Global perceived effect will be analyzed for 3,6,12 months on a 5 point scale using categorical data analysis.

Pain medication log at baseline, 3, 6, and 12 months will be analyzed by a simple categorical decrease, increase, or unchanged compared to baseline. Morphine equivalents will not likely be helpful as the majority of the subjects will not likely be on opiate medication. Those patients not on medication at baseline shall not be included in the medication analysis.

Adjunctive treatments: All other therapeutic treatments for LBP during the study period shall be recorded at 3, 6 and 12 months.

5C. Monitoring:

Patients will be contacted by telephone during post-treatment week one to monitor for any concerning symptoms or adverse events. The patient will be seen in follow-up at approximately 2 weeks and 4 weeks post-treatment to assess for any adverse events. Patients will also be seen 2 months, 3, 6, and 12 months post-treatment for evaluation and data collection or more frequently if clinically necessary. Patients will be made aware by verbal and written instructions that they have phone access to the study physicians at any time and are instructed to contact the practice for any concerning symptoms. These include redness at the injection site, swelling, fever, bowel or bladder problems, worsening of low back symptoms beyond day 2 post-procedure, severe low back pain at any time, and new or worsening of any lower extremity symptoms. Any new or worsening lower extremity symptoms such as pain, numbness, or weakness will be evaluated clinically, and if needed, further diagnostic tests such as MRI or electrodiagnostic testing will be ordered. Any significant increase in low back pain or fever, without an identified source in the 7-30 days post intradiscal treatment shall be considered suspicious for discitis. CBC with differential, C-reactive protein, sedimentation rate, as well as MRI shall be performed (CT or bone scan if contra-indications to MRI exist).

Any severe adverse event deemed specifically related to the bone marrow concentrate injectate shall be reported within 24 hours to the IRB (see adverse events 6C).

5D: Storage of data

The research data will be stored in paper files accessible only to the investigators as well as research clinical staff under direct supervision of the investigators. The data will be kept secure in a locked cabinet when not in use.

5E. Confidentiality of data

Data will be kept in a secure location following all HIPAA standards.

Patients will be assigned a subject number and data will correspond to such number and not any identifiable demographic data.

6. Risk/Benefit assessment

6 A. Risks of participation in the study

Physical risks:

Risks specific to bone marrow aspiration:

These risks include bleeding, infection and damage to nearby tissues, vessels, nerves or organs. Other very unlikely risks include injury to the bone itself including fracture and continued pain in the region. Extremely unlikely risks include: paralysis, cardiac arrest, brain damage and/or death. Estimated risk of minor complication is less than 1%. Estimated risk of a catastrophic complication is near zero.

Risks specific to placebo bone marrow aspiration:

These risks include bleeding, infection and damage to nearby tissues, vessels, nerves or organs. Estimated risk of minor complication is less than 1%. Estimated risk of a catastrophic complication is near zero.

Risks of intradiscal delivery of the BMC, i.e. the injection procedure itself, are considered equivalent to the risk of discography and are as follows:

- Nerve injury, in particular the exiting ventral ramus. Risk is considered extremely low in an awake patient either with no sedation or appropriate conscious sedation [28]
- Discitis with a risk of 0% to 1.3% per disc [41]
- Theoretical risk of bowel injury and nerve root injury are considered an anatomic impossibility unless a grossly inappropriate technique is used. Estimated risk is near zero. [28]
- Theoretical risk of needle passage through the dura may be estimated at 3% based upon data from a retrodiscal transforaminal epidural steroid injection approach [36]. The risk of this being clinically significant is less than 1% [28].

- The risk of clinically significant bleeding during discography in a non-anticoagulated patient is exceedingly rare and is estimated at less than 1%.
- Severe allergic reactions to the contrast dye, local anesthetic, or antimicrobial skin prep are rare and are estimated at less than 1%.
- Vaso-vagal reactions in a non-sedated patient are estimated at 3-4%. In an awake but sedated patient, the risk is estimated at 0-10% [42].
- Risks of the use of needles include local muscle pain [28].
- The risk of needle puncture to a disc includes acceleration of disc degeneration and increased risk of disc herniation over a 10 year period. Risk is considered minimal but statistically significant over control [32].
- The risk of accelerated disc degeneration secondary to contrast medium placed into the disc. Possible injury to intervertebral disc cells has been demonstrated experimentally [43]. Clinical implications are questionable. Risk is considered very minimal and is estimated at less than 1%.
- General risks of disc injections include the exceedingly rare risk of paralysis or death. Estimated near zero.
- General risks of conscious sedation (if utilized) include respiratory depression, cardiac arrhythmia or arrest, stroke, or death. Estimated risk is far less than 1%.
- Risk of venipuncture for IV sedation for the BMC injection procedure (if utilized): The risks of IV access include infection, bleeding, and nerve injury. The risks of the sedation medication itself include low blood pressure, low oxygen level, depression of the respiratory drive, cardiovascular compromise, stroke, severe allergic reaction, and death.

Risks of bone marrow concentrate within the disc:

- The injectate is an autologous aspiration of bone marrow minimally altered through a centrifuge process. No reported side effects beyond local soreness have been reported in other tissues or the spine. Bone marrow concentrate does contain stem cells. The theoretical risk of the development of a neoplasm does exist however unlikely. These are non-cultured stem cells and therefore, should hold the same risk for tumor development as those naturally occurring. A registry surveillance study which included follow-up MRI's did not reveal any evidence tumor development [22]. However, we do not assume the risk of injury to the disc tissue is zero. Risk is unable to be quantified but assumed much less than 1%.
- Risk of BMC in the epidural space. With disc injections, leakage may occur into the epidural space. Whole blood is commonly injected into the epidural space for the

purpose of treatment of spinal headache. Although we would not anticipate a tissue response different from whole blood, we do not assume risk of injury to the neural structures and dural tissue is zero. Although there is not extensive data on the effect of BMC on nervous tissue, bone marrow has been used extensively during spinal fusion procedures without any reports of complications attributed to the bone marrow itself [17,18]. Risk is unable to be quantified but assumed much less than 1%.

- The risk of anticoagulant acid citrate dextrose (ACD) used in the processing of the BMC: ACD is an FDA approved anticoagulant most often used to prevent clotting of blood samples. It is commonly used in blood transfusions as well as hemodialysis in heparin intolerant patients. The amount of ACD remaining available within the BMC to be injected is very small. Risks are as follows: hypocalcemia, bleeding, severe allergy. Risk is unable to be quantified but assumed to be much less than 1%.

The risk of heparin used to prime the needle, syringes and BMC filtering and processing containers of the BMC: heparin is an FDA approved anticoagulant most often used to prevent clotting. It is commonly used clinically at much higher dosages.

Risks of placebo treatment procedure: an intramuscular injection of normal saline.

- Risk of infection for an intramuscular patient estimated at much less than 1%.
- Risks of the use of needles for an intramuscular injection of contrast and then normal saline include local minor skin puncture and muscle pain [28].
- Severe allergic reactions to the contrast dye, local anesthetic, or antimicrobial skin prep are rare and are estimated at less than 1%.
- Risk of venipuncture for IV sedation for the injection procedure (if utilized): The risks of IV access include infection, bleeding, and nerve injury. The risks of the sedation medication itself include low blood pressure, low oxygen level, depression of the respiratory drive, cardiovascular compromise, stroke, severe allergic reaction, and death.

Vaso-vagal reactions in a non-sedated patient are estimated at 3-4%. In an awake but sedated patient, the risk is estimated at 0-10% [42].

The psychological risk does involve the emotional and physical discomfort of undergoing a bone marrow aspiration and an intradiscal procedure or placebo procedure.

Social and legal risks are considered minimal.

Economic risk: Considered minimal. There will be no cost to the patient except for routine follow-ups including co-pays and deductibles from commercial insurance.

6 B. Prevention of risks:

The risks of the delivery of the BMC into the disc will be reduced by following strict sterile technique as well as procedural technique as described in SIS guidelines [28]. Prophylactic antibiotic will be placed into the disc to minimize the risk of discitis.

The discomfort of the procedure shall be minimized with by oral or IV sedation unless the patient prefers no sedation. Intravenous or IM fentanyl may be given for intra-procedural pain control. Local anesthetic, 2-5ml lidocaine 1%, shall be infiltrated in the skin and superficial tissues. Local anesthetic, 1ml 2% may be placed outside the disc to minimize the discomfort of the disc injection. Ropivacaine 0.2- 1% may be placed within the disc as well.

The patients will be monitored for adverse events as previously described.

6C. Adverse events:

Adverse events include:

- Infection including discitis
- Bleeding, in particular, an epidural hematoma
- New and/or increased pain, numbness, dysesthesia, or weakness in one or both lower extremities
- Increased low back pain beyond normal flares typical for the patient
- Allergic reaction
- Fever
- Redness at injection site
- Bowel or bladder dysfunction
- Paralysis
- Death

Any minor adverse event will be reported to the IRB within 10 days. Any serious adverse event will be reported to the IRB within 24 hours of being brought to an investigator's attention.

Our medical staff will be available at all times for any adverse event. If subsequent diagnostic tests or procedures are necessary they will be in accordance with current standard of care. All patients will have medical insurance coverage for any subsequent tests or procedures. BMC is an autologous tissue product with multiple medical uses. Intradiscal administration should not preclude insurance coverage for any subsequent medical issues pertaining to its use.

6D. Benefits:

The potential benefits of participating in the study are significant. The patient has an opportunity to significantly reduce or alleviate his or her pain and disability with a relatively minimally invasive procedure compared to fusion surgery. The benefits to the community as a whole could be significant as well, potentially decreasing or even eliminating the need for surgical fusion for discogenic pain.

7. Participant recruitment and informed consent

7A. Recruiting: Patients will be screened from a pool of existing patients at a community outpatient spine and musculoskeletal practice. Patients referred by outside clinicians may be considered. These patients will have had an inadequate response to conservative treatments, many of whom will be considering fusion surgery. Some of these patients may be considering provocative discography through the recommendation of one of the physicians in the principle investigator's practice or from a local surgeon. One of the options discussed will be Bone marrow concentrate intradiscal injection under the context of the study. If the patient has any interest in participating in this study, the general risks, benefits and results from the previously published study for intradiscal BMC will be discussed [24,25]. Some of these patients may wish to undergo discography. The results of the discography help determine their candidacy for fusion surgery. Patients who have undergone discography at the request of an outside physician, typically a community neurosurgeon or orthopedic surgeon, will also be screened with the surgeon's approval.

It will be explained to all potential subjects that their participation in the study is strictly voluntary. Their participation will have no effect on their standing as a patient within their current practice. Nor will it have any effect on the physician-patient relationship. Their treatment course will remain unaffected if they choose not to participate in the study.

7B. Consent:

Consent form as a separate document submitted with this document.

7C. Obtaining and documenting consent

One of the investigators will perform the consent process. This will be verbal and written with ample time for any and all questions. The consent form will be signed by the patient and witnessed by one of the research assistants and/or one of the investigators. The document will be stored with other research materials in a locked cabinet when not in use.

7D. Participant comprehension and capacity

Measure to ensure appropriate understanding:

Prior to signing the consent form, the patient will be asked to briefly explain the study risks and benefits to one of the investigators.

7 E. Cost to participant

As previously mentioned in economic risk section:

This will be a funded study without cost to the participant other than co-pays and deductibles from commercial insurance for routine follow up visits.

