- Chronic low back pain greater than 6 months with low back pain component greater than leg pain component if present.
- Average pain at least 40/100 on Visual analogue Scale (VAS)

- Inadequate response to conservative care including medication, physical therapy, and/or spinal injections.
- Males and females at least 18-55 years old.
 - Rationale for age limit of 55: Based upon the study by Depalma et al. [27], at age 55 and less the predicted probability of a discogenic source of pain is higher than any other source. Beyond 55 years of age, zygapophyseal joints have a higher predictive probability. Therefore, the pre-test probability for a test for discogenic pain beyond this age is considerably lower.
- Have provided informed consent.
- If female subjects are of child-bearing potential, they must be using an acceptable form of birth control.
- Advanced imaging of MRI or CT demonstrating abnormal disc morphology.
- Presumed lumbar discogenic pain based upon either A or B below:
 - A. Positive provocative discography in accordance with SIS guidelines [28].
 - Or
 - B. Both B1 and B2
 - B1. The patient must have MRI findings suggestive of discogenic low back pain including either a high intensity zone region or type 1 or type 2 end plate Modic changes [29-31].
 - B2. Exclusion of other structures as source of pain (see below).

Rationale for not requiring discography for inclusion:

The rationale involves several factors. Although injecting the BMC at the time of discography seems most reasonable, the volume of contrast used for the discography test may reach 3ml, when performed in accordance with SIS guidelines [28]. This leaves an inadequate volume capacity to accommodate much volume of BMC. Secondly, in accordance with SIS guidelines [28] discography requires a negative control disc. Discography is invasive and may have negative detrimental effects on the disc [32]. Therefore, potential harm may exist if discography is performed. BMC is considered to be a very benign substance; it is an autologous tissue unlikely to have any detrimental effects [17, 18, 22].

Subjecting patients to two distinct intradiscal procedures (discography prior to the BMC procedure) is difficult to justify when the purpose of discography

(including injecting a normal control level) would be for qualification of an intradiscal injection of a very likely benign substance.

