With two treatment patients for each placebo patient, 40 treatment and 20 placebo patients will be required to achieve 80% power to detect a difference of 0.35 in the proportion of patients with successful improvement between groups with a chi-squared test at a level of significance of 0.05, assuming the proportion of patients achieving success in the control group is 0.2 (20%) This is based upon the preliminary data calculated success rate (>50% improvement in Pain) from Pettine et al. study [24] was 61%. (Our calculation differs from Pettine et al. as we included surgical patients as failures.) The 95% CI are 44-75% using an n of 40 in our proposed treatment group. The placebo rate is a very well done spinal explanatory study was 13% [33]. The placebo rate from an intradiscal study using intradiscal normal saline was 12.5% and 23.5% using hyaluronic acid (the carrier for the treatment). We therefore used the conservative estimate of a placebo response rate of 20% in this study.

5. Study design/methods/procedures

5A. Summary of research design

A total of 60 patients with randomization 2:1 ratio (treatment : control). Pain and function will be assessed using VAS and ODI. Primary outcome will be percentage of patients in the treatment group compared to the control group at 6 months categorized as a clinical success, at least 50% relief of pain. Secondary outcomes will be comparison of success rates (at least 50% pain relief) at 3 and 12 months. Other secondary outcome will be percentage of patients in the treatment group vs control group with greater than 30% improvement in ODI at 3, 6, and 12

months. Global Perceived Effect (GPE) will also serve as a secondary out come at 3, 6, and 12 months. Medication log and adjunctive treatments will also be recorded and analyzed.

| Randomization process: computer randomization program

Randomization shall be performed through a computer randomization program.

<https://www.random.org/#numbers> (Randomness and Integrity Services Ltd. Dublin, IR.) A random number shall be generated between 1 and 60. For all randomly generated number from 1 to 40, the patient will be assigned to the treatment group. For all randomly generated random number from 41 to 60, the patient shall be assigned to the placebo group.

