The patients will be blinded to treatment assignment. The patient will follow up for assessment with an investigator who remains blinded to the treatment assignment. Only the physician performing the procedure will be aware of the group assignment.

Based upon previous recommendations for the assessment of blinding success in clinical trials [34] the patients will be queried at 2 weeks whether they believe they have received the active treatment, the placebo, or if they do not know to which group they were assigned.

Treatment: a single intradiscal injection of autologous bone marrow concentrate into suspected painful discs based upon history, image findings and the exclusion of other anatomic structural sources of pain such as z-joints and SIJ.

Placebo: Intramuscular injection of normal saline directly above the transverse process at each suspected discogenic pain level. (The physician performing the procedure will not be blinded, but the assessor for follow up evaluation will be blinded).

A sham bone marrow aspiration will also be performed involving fluoroscopic guidance and anesthetic to the iliac crest. The patient will hear the noise of the bone marrow drill (unattached), while a 21 gauge needle is tapped against the periosteum.

Patients will be screened from a pool of existing patients at a community outpatient spine and musculoskeletal practice. These patients will have had an inadequate response to conservative treatments, some of whom will be considering fusion surgery. Some of these patients will be considering provocative discography through the recommendation of a local surgeon. One of the options discussed will be bone marrow concentrate intradiscal injection under the context of the study. If the patient has any interest in participating in this study, the general risks, benefits and literature will be discussed. The patient will be informed that their status as a patient in the principle investigator's practice and the physician-patient relationship will not be altered regardless of their participation in the study. They will be given a written summary of the study. If they have continued interest, an appointment will be arranged for the verbal and written consent process. Once the consent form process has been completed, the patient will perform the VAS as well as the ODI which will serve as the baseline measurement data [35]. A pain medication query shall be performed as well.

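### The mean-pain t-tests in 5B do not say which scores they use, and no baseline-adjusted model is named; ANCOVA on the same data would usually be more precise

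*Combined protocol and SAP*

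**What the plan says.** The whole plan for mean pain is one sentence in section 5B: "Group data mean pain scores will also be analyzed for each time point using" t-tests. The section opens with "The data from the pre and post VAS (0-100 mm) and Oswestry disability index 0-100 will be analyzed from baseline" and then names the three follow-up visits, but defines no change score and no model.

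Baseline VAS is available for everyone. Section 5A says that after consent "the patient will perform the VAS as well as the ODI which will serve as the baseline measurement data", and its follow-up schedule repeats it: "At baseline 3,6,and 12 months the patients will complete the VAS, ODI and Global Perceived effect" (GPE is not done at baseline). Section 4A requires average pain of at least 40/100 at entry.

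Neither ANCOVA nor any other regression or mixed model appears in the document. Mean pain is not among the outcomes listed in 5A. The primary outcome is a responder rate: "Primary outcome for success will be considered at least 50% improvement in pain by VAS at 6 months".

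**The concern.** Three analyses fit the wording. The reference to mean scores at each time point suggests raw follow-up values. The section's opening, with pre and post scores taken from baseline, suggests change scores or a paired test. The t-test sentence names no comparator, so a paired test within each arm is not excluded, and that would not compare the arms at all.

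The choice matters because the arms may differ in baseline pain by chance. The randomisation in 5A describes no stratification on pain, and the placebo arm has 20 patients. If the treatment arm happens to start with more pain, a raw-score comparison is pushed against treatment and a change-score comparison in its favour. Two analysts who both follow the protocol could report different answers from the same data.

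Both between-arm t-tests are unbiased over repeated randomisations, so this is not a validity error. What is at stake is the precision and definition of the only planned comparison that uses pain as a continuous measure.

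**Working it through.** The plan states no figure for the mean-pain comparison, so there is none to reproduce.

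**Inputs from the document.** 40 treatment and 20 placebo patients (4F, 5A); VAS at baseline, 3, 6 and 12 months (5A); entry floor of 40/100 (4A).

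**Assumptions, not in the document.** Correlation r between baseline and follow-up VAS of 0.3 to 0.6; ratio k of baseline SD to follow-up SD equal to 1, with 0.7 as a second case; true effect 0.7 follow-up SD; two-sided 0.05; the same SD and slope in both arms; no dropout.

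**1. Chance baseline imbalance.** SE of the baseline difference = sqrt(1/40 + 1/20) = 0.274 SD. The two-sided normal probability is 0.361 beyond 0.25 SD (0.25/0.274 = 0.91) and 0.100 beyond 0.45 SD (0.45/0.274 = 1.64).

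**2. What a 0.45 SD imbalance does.** A raw-score difference moves by r × 0.45. A change-score difference moves by (r − k) × 0.45. In follow-up SDs:

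| r | Raw | Change, k = 1 | Change, k = 0.7 |
|---|---|---|---|
| 0.3 | +0.135 | −0.315 | −0.180 |
| 0.4 | +0.180 | −0.270 | −0.135 |
| 0.5 | +0.225 | −0.225 | −0.090 |
| 0.6 | +0.270 | −0.180 | −0.045 |

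**3. Variance of the between-arm difference, relative to raw scores.** Raw = 1. Change = 1 + k² − 2rk. ANCOVA = 1 − r² in large samples, multiplied by 1 + 1/56 here for estimating the slope. The large-sample excess of change over ANCOVA is (k − r)²/(1 − r²).

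| r | ANCOVA, large sample | ANCOVA, N = 60 | Change, k = 1 (excess) | Change, k = 0.7 (excess) |
|---|---|---|---|---|
| 0.3 | 0.91 | 0.93 | 1.40 (54%) | 1.07 (18%) |
| 0.4 | 0.84 | 0.86 | 1.20 (43%) | 0.93 (11%) |
| 0.5 | 0.75 | 0.76 | 1.00 (33%) | 0.79 (5%) |
| 0.6 | 0.64 | 0.65 | 0.80 (25%) | 0.65 (2%) |

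**4. Power and interval width.** Noncentral t, with noncentrality 0.7/(0.274 × square root of the relative variance); 58 df for the t-tests, 57 for ANCOVA with the N = 60 variance.

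| r | Raw | Change, k = 1 | Change, k = 0.7 | ANCOVA | ANCOVA CI width / raw CI width |
|---|---|---|---|---|---|
| 0.3 | 71.0% | 56.5% | 68.1% | 74.2% | 0.963 |
| 0.4 | 71.0% | 63.1% | 74.1% | 77.6% | 0.925 |
| 0.5 | 71.0% | 71.0% | 80.7% | 82.0% | 0.874 |
| 0.6 | 71.0% | 80.2% | 87.6% | 87.6% | 0.807 |

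**5. Low correlation.** ANCOVA power is 72.0% at r = 0.2, 71.2% at r = 0.15 and 70.2% at r = 0, against 71.0% for raw scores throughout.

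**6. Simulation.** With 20,000 simulated trials of 40 and 20 patients at each r (k = 1), power was 74.4, 77.3, 81.9 and 87.7% for ANCOVA and 56.8, 62.8, 70.9 and 80.1% for change scores, within one point of the formulas.

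**The case against.** The strongest reply is that little hangs on this. Mean pain is not a listed outcome, the sample size does not rest on it, and 5B adds it after all the responder analyses. An unadjusted between-arm t-test is valid, so preferring ANCOVA is a gain in efficiency and not the repair of an error. Baseline also enters the plan elsewhere, since each VAS and ODI success criterion is a percentage improvement. The sentence before the t-tests compares success rates with placebo, so a between-arm test is the natural reading and the paired reading the least likely. Finally, the size of the gain comes from assumed values.

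Most of this stands, and it limits the weight of the point. The entry floor of 40 may lower the correlation and shrink the baseline SD. At k = 0.7 the power gap between change scores and ANCOVA falls from about 18 points to 6 at r = 0.3, and vanishes at r = 0.6. Against raw scores the gain is 3 points at r = 0.3 and 1 point at r = 0.2.

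The reply does not settle which t-test is meant. Even if the test is taken as between arms, raw and change scores both remain open and pull in opposite directions under imbalance. Nor does it give a reason to leave out a baseline value that is already collected.

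**Conclusion.** The concern holds. The form of the mean-pain test is not stated, no baseline-adjusted model is named, and ANCOVA would usually be the more precise choice. Under equal SDs and correlations of 0.3 to 0.6, its variance is 9 to 36% below the raw-score test in large samples (about 7 to 35% at N = 60), its interval is 4 to 19% narrower, and a change-score test carries 25 to 54% more variance. If the baseline SD is 0.7 of the follow-up SD, that last range falls to 2 to 18%. Against raw scores there is essentially no gain below a correlation of about 0.15.

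The power figures also rest on an assumed 0.7 SD effect and serve only as a scale for comparing methods, since the plan sets no power target for mean pain. The change is worth making for a supportive analysis; the primary conclusion does not depend on it.

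**What to change.** In 5B, replace the mean-pain t-tests with: *Mean VAS at 3, 6 and 12 months will be compared between arms by ANCOVA with treatment arm and baseline VAS as terms, reporting the adjusted mean difference and its 95% CI.*

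A single repeated-measures model with baseline VAS, arm, visit and arm-by-visit interaction is an alternative that also uses patients with partial follow-up. If the t-test is kept, state that it compares the arms and whether it uses raw or change scores; this removes the ambiguity but forgoes the usual gain in precision.

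The cost is one sentence and no new data. If baseline turns out to be uncorrelated with follow-up, power relative to a raw-score test falls from 71.0% to 70.2% under the assumptions above.
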